14.6. Investigator Training

Device and database training will be provided to all the participant investigators and support staff prior to patient enrollment in the trial. Device training will be conducted at the TransMedics or equivalent training facility. Database training will consist of an explanation of the structure of the database, the data elements to be collected, simulated use of the database, error handling, and instructions regarding the handling of queries. Device training will include the following:

- A didactic session, where the investigators will be introduced to the device and its use model through presentations and videos.
- Hands-on experience.

The Sponsor will perform animal procedures to train investigators on the device as follows:

- Device set-up, that includes system check, installation and priming of the Lung Perfusion Set.
- Lung instrumentation on the device that includes cannulation of the donor lung and subsequent instrumentation of the lung on the device. It also includes adjustment of different parameters such as gas flow rate, temperature and blood flow rate of the blood and solution perfusate as recommended in the IFU.
- Cessation of lung perfusion and removal from the device by using appropriate solutions and then terminating the circulatory pump.

15. INVESTIGATIONAL SITE TERMINATION

The Sponsor may terminate an investigational site from the study for any of the following reasons:

- Repeated failure to complete case report forms
- Failure to obtain Informed Consent
- Failure to report Serious Adverse Events

- Loss of or unaccountable investigational device inventory
- Repeated protocol violations
- Failure of investigator to comply with training or IFU
- Failure to follow patient management guidelines

17. AMENDMENT POLICY

The investigator will not make any changes to this plan without prior written consent from the Sponsor and subsequent approval by the IRB or EC, except if the deviation from the protocol is necessary to protect the life and physical well-being of a subject in an emergency. Such protocol deviations will be reported to the Sponsor and the reviewing IRB or EC as soon as possible, but no later than 5 working days after the emergency occurred.

Any permanent change to the protocol, whether it is an overall change or a change for specific trial center(s), will be handled as a protocol amendment. Any amendment to the protocol that appears indicated as the trial progresses will be fully discussed by the investigator(s) and the Sponsor. If agreement is reached regarding the need for an amendment, it will be written by the Sponsor. The written amendment will be submitted to the chairman of the IRB or EC responsible for reviewing amendments.

Except for "administrative letters," investigators will await IRB or EC approval of protocol amendments before implementing the change(s). Administrative letters are defined to have no effect on the validity of the data or information resulting from the completion of the approved protocol, or the relationship of likely patient risk to benefit relied upon to approve the protocol; the scientific soundness of the investigational plan or protocol; and, the right, safety or welfare of the human subjects involved in the investigation. The Sponsor will notify the FDA of such changes in a 5-Day Notice. When, in the judgment of the IRB or EC, the investigators and/or the Sponsor, the amendment to the protocol substantially alters the trial design and/or increases the potential risk to the subject; such changes will be approved by the FDA and the IRB and EC.

2. If the patient was extubated, the PGD will be graded 0 or 1 based on absence or presence of infiltrates and/or edema on chest radiograph.
3. All ECMO use will be graded as grade 3 except for pre-specified center specific protocol ECMO for pulmonary hypertension and/or hemodynamic support.¹

These criteria will be applied at the T0, 24, 48, and 72-hour timepoints after transplantation according to ISHLT guidelines.

PGD Assessment Timepoints Definition

PGD Assessment Timepoint	Definition
T0	At the time of ICU admission post-transplant
T24	24 hours post-transplant*
T48	48 hours post-transplant*
T72	72 hours post-transplant*

* Use closest value to these timepoints.

¹ In addition, TransMedics will perform two additional exploratory analyses: (1) analyze the PGD results with patients on pre-specified center-specific ECMO excluded (ungradeable) and (2) analyze the PGD results with patients on pre-specified center-specific ECMO graded as PGD3.

**APPENDIX 2. PATHOLOGIC GRADING OF LUNG REJECTION
(MARTINU, 2009)**

Category	Grade	Meaning	Appearance
A: Acute Vascular Rejection	A 0	None	Normal lung parenchyma
	A1	Minimal	Inconspicuous small mononuclear perivascular infiltrates
	A2	Mild	More frequent. More obvious, perivascular infiltrates, eosinophils may be present
	A3	Moderate	Dense perivascular infiltrates, extension into interstitial space, can involve endothelialitis, eosinophils, and neutrophils
	A4	Severe	Diffuse perivascular, interstitial, and air-space infiltrates with lung injury. Neutrophils may be present.
B: Acute Airway Inflammation	B0	None	No evidence of bronchiolar inflammation
	B1R	Low grade	Infrequent, scattered or single layer mononuclear cells in bronchiolar submucosa
	B2R	High grade	Larger infiltrates of larger and activated lymphocytes in bronchiolar submucosa. Can involve eosinophils and plasmacytoid cells.
	BX	Upgradable	No bronchiolar tissue available

APPENDIX 3. PRIMARY SAFETY ENDPOINT

The primary safety endpoint is the number of lung graft-related serious adverse events through the 30-day follow-up after transplantation per subject. This endpoint is defined to consist of the following adverse events (at most one per type), if they are serious adverse events (see below):

- **ACUTE REJECTION (Biopsy proven greater than grade A2):** Defined as moderate or severe according to the ISHLT working formulation of Pathologic grading listed in [Appendix 1](#) of this protocol.
- **RESPIRATORY FAILURE:** Defined as Impairment of respiratory function requiring re-intubation, tracheostomy or the inability to discontinue invasive ventilator support within 4 days (96 hours) post-transplant. This excludes intubation for re-operation or temporary intubation for diagnostic or therapeutic procedures. (Slightly modified from Intermacs²).
- **BRONCHIAL ANASTOMOTIC COMPLICATION:** Defined as moderate to severe necrosis (mucosal and/or extending to bronchial wall) at the bronchial anastomotic site due to ischemic injury, with or without bronchial anastomotic dehiscence (Grade II – IV) as visualized by flexible fiber optic bronchoscopy and/or chest CT (for dehiscence), and/or requiring antibacterial/antifungal treatment, chest tube placement (tube thoracostomy), uncovered metallic stent placement, primary repair, open surgical repair, pneumonectomy, or re-transplantation. Bronchoalveolar (BAL) specimen/culture should be obtained if evidence of focal infection prior to initiating treatment. (Santacruz 2009, Van de Wauwer 2007).
- **MAJOR PULMONARY-RELATED INFECTION:** Defined as a clinical infection of lung origin that is treated with antibacterial/antifungal/antiviral agents (non-prophylactic). This category includes, but is not limited to: bacterial pneumonia/tracheobronchitis (*Pseudomonas aeruginosa*, coagulase-positive and coagulase-negative *Staphylococcus* species (including MRSA), *Chlamydia pneumoniae*, *Enterococcus* (including VRE), *Enterobacteriaceae*), Cytomegalovirus (CMV) pneumonitis/pneumonia, Herpes Simplex Virus (HSV) tracheobronchitis/pneumonitis/pneumonia, Aspergillus tracheobronchitis/pneumonia, and aspiration pneumonia/pneumonitis. Presence of pulmonary infiltrate(s) on chest x-ray along with a positive BAL specimen/culture, or positive sputum culture, or positive fungal staining/culture, and/or chest CT, and/or transbronchial biopsy specimen to confirm infection and rule out rejection should be present unless strong clinical evidence indicates the need for treatment despite negative cultures. CMV diagnosis requires BAL for cytology or transbronchial biopsy specimen. Diagnosis of Aspergillosis requires fungal histopathology and/or culture of BAL/tissue specimen, bronchoscopic findings consistent with the disease, and possible chest CT. Paradis 1993, Maurer 1992, Horvath 1993, Zamora 2004, Singh 2003, Silveira 2008, Lau 2004, Kotloff 2004).

Serious Adverse Event (SAE) Definitions:

² Intermacs (Interagency Registry for Mechanically Assisted Circulatory Support) <http://www.intermacs.org/>

An adverse event will be classified as serious if it meets any of the following criteria:

- Results in, leads to, or contributes to, a death
- Is life-threatening
- Results in permanent disability or incapacity (i.e., permanent impairment of a body function or permanent damage to a body structure)
- Requires patient re-hospitalization or prolongs initial hospitalization
- Necessitates medical or surgical intervention to preclude a permanent disability or incapacity
- Results in fetal distress, fetal death or a congenital anomaly/birth defect.

APPENDIX 4. SCHEDULE OF CLINICAL ASSESSMENTS

Evaluations	Donor & Lung Assessments	
	At Acceptance	OCS Preservation
Eligibility & ID	X	
Demographics/Characteristics	X	
Donor Cause of Death	X	
Donor Medical History	X	
Initial & Final Blood Gas and PaO ₂ /FiO ₂ Ratio at donor's offer	X	
Ventilation Settings at Final Blood Gas in donor's offer	X	
Final Chest X-ray report/findings	X	
Final Bronchoscopy Findings	X	
Cross Clamp Time and Flush Details		X
Donor Allocation Status		
OCS Pre-Instrumentation ABG (Priming)		X
OCS Instrumentation Details (Date and Time)		X
OCS Preservation Parameters		X
OCS Final Assessment		X
Device Malfunction (if applicable)		X
Non-transplant Reasons (if applicable)		X

Evaluations	Recipient Schedule of Assessments						
	Day of TX	T0	T24	T48	T72	Day 7	Discharge
Eligibility & Informed Consent	X						
Demographic/Characteristics	X						
Etiology of Lung Failure	X						
Medical History including Cardiac	X						
Transplant Details	X						
PGD Scores	X	X	X	X	X		
Mechanical Circulatory Support & Reason	X	X	X	X	X	X	X
Invasive Ventilator Support	X	X	X	X	X	X	X
Patient Survival						X	X
Graft Survival						X	X
Bronchoscopy, BAL & Biopsy					X	X*	X*
Pulmonary Function Test					X**	X*	X*
Immunosuppressive Meds & Induction (if applicable)	X			X	X		
ICU & Hospital Stay	X	X	X	X	X	X	X
Lung Graft-Related SAE's	X	X	X	X	X	X	X
All SAE's & Associated Meds	X	X	X	X	X	X	X
Diagnosis of BOS						X	X

* ONLY tests regularly scheduled per center standard of care or performed due to a clinical cause at these timepoints will be collected.

** Pulmonary Function Test can be done within the first 90 days post transplant according to patient's condition. If not done reason will be specified and recorded.

**APPENDIX 5. DRAFT PATIENT INFORMED CONSENT FORM
TEMPLATE**

(This Page is Intentionally Left Clear)

APPENDIX 6. DRAFT CASE REPORT FORMS

(This Page is Intentionally Left Clear)

**LIST OF ABBREVIATIONS**

Term	Definition
ABG	Arterial Blood Gas
AE	Adverse Event
BOS	Bronchiolitis Obliterans Syndrome
DCD	Donation after Cardiac Death
ECMO	Extracorporeal Membrane Oxygenation
EVLP	Ex-Vivo Lung Perfusion
FiO 2	Fraction of inspired oxygen
ICU	Intensive Care Unit
IFU	Instructions for Use
LAS	Lung Allocation Score
MedDRA	Medical Dictionary for Regulatory Activities
OCS	Organ Care System
PaO 2	Partial pressure of O 2 in arterial blood
PAP	Pulmonary Artery Pressure
PCWP	Pulmonary Capillary Wedge Pressure
PEEP	Positive End Expiratory Pressure
PGD	Primary Graft Dysfunction
PP	Per Protocol
PT	Preferred Term
SAE	Serious Adverse Event
SOC	System Organ Class
T0, T24, T48, T72	Time after transplant (0, 24,48, 72 hours)

## 1. INTRODUCTION

This analysis plan provides a detailed description of the safety and effectiveness analyses, summary tables, and by-patient data listings planned in the analysis of the data in the OCS-LUN-012017 study ["International Trial to Evaluate the Safety and Effectiveness of the Portable Organ Care System (OCS™) Lung System for Recruiting, Preserving and Assessing Non-Ideal Donor Lungs for Transplantation (EXPAND II Trial)", [REDACTED]].

## 2. STUDY OBJECTIVE

The objective of this study is to evaluate the safety and effectiveness of the OCS™ Lung System to recruit, preserve and assess donor lungs that may not meet current standard donor lung acceptance criteria from one or more of the following characteristics:

- Donor  $\text{PaO}_2/\text{FiO}_2 \leq 300$  mmHg at the time of the offer; or
- Expected cross-clamp time of  $> 6$  hours for the second lung; or
- Donor after Cardiac Death (DCD donor); or
- Donor age  $\geq 55$  years old.

## 3. STUDY DESIGN

### 3.1. Overview

This is a prospective, pivotal, international, single-arm trial of donor lungs and donor lung transplant recipients.

The proposed clinical trial seeks to evaluate the safety and effectiveness of the OCS™ Lung System for donor lungs that today may not be transplanted due to the limitations associated with cold storage technique (such as ischemia and the inability to evaluate organ function following cold preservation). The results of the OCS™ Lung System with non-ideal donor lungs in this study will be compared to the results for both the control arm of the INSPIRE trial and to the results of the NOVEL study of the XEVIVO EVLP system.

Subjects will be followed for up to 36 months from the date of transplantation. The details of the follow-up are summarized in Appendix 4 of the Protocol as follows:

- All subjects will be followed from transplant to discharge.
- Patient survival will be documented on Day 30 post-transplant and at initial hospital discharge following transplantation (if longer than 30 days).
- Patient survival and clinical diagnosis of BOS will be documented at 6, 12, 24, and 36 months patient follow-up (these are post-market follow-up timepoints) per Appendix 4 of the Protocol.

### **3.2. Method of Assigning Subjects to Treatment**

Not applicable.

### **3.3. Blinding**

Not applicable.

### **3.4. Determination of Sample Size**

The sample size for this trial was determined based on providing adequate statistical power for hypothesis testing of the two co-primary effectiveness endpoints. All sample size calculations were performed using PROC POWER in SAS.

For the first co-primary endpoint, the calculations assumed a one-sided exact binomial test, an alpha level of 0.025, a control-based rate of 0.939 with a margin of 0.12 (to derive the performance goal of 0.819), a true survival rate for OCS™ of 0.939, and desired power of 90%. Based on these specifications, the required sample size was determined to be 84 transplanted recipients.

For the second co-primary endpoint, the calculations assumed a one-sided exact binomial test, an alpha level of 0.025, a performance goal of 0.54, a utilization rate of 72% for OCS™, and desired 90% power. Based on these specifications, the required sample size was determined to be 84 transplanted recipients

In order to ensure that a sufficient number of subjects are evaluable in the per-protocol population of the trial, 90 transplanted recipients in the study are expected to provide adequate power to evaluate the two co-primary effectiveness objectives given the assumptions described.

Due to multiple primary endpoints, the Hochberg Method will be used to control familywise error. The p-values for each of the co-primary endpoints will be ordered from highest to lowest. If the highest p-value is less than 0.025 then both endpoints achieve statistical significance and the null hypothesis of each co-primary endpoint can be rejected. If not, then the lower of the two p-values will be assessed against a significance level of 0.0125. If the adjusted significance level of 0.0125 is applied to any of the co-primary endpoints, the power of that analysis will be greater than 85%. Therefore, the study will be considered successful in either of the two scenarios described above.

With regard to the primary safety endpoint, the pre-specified safety margin of 0.7 events per patient, the estimated mean of 0.29 events per patient (with an estimated standard deviation of 2.0), a one-sided alpha of 0.025, and the sample size of 90 transplanted recipients results in power greater than 90% when considering a one-sample t-test on the mean.

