9.7. Sample Size Determination

The sample size for this trial was determined based on providing adequate statistical power for hypothesis testing of the two co-primary effectiveness endpoints. All sample size calculations were performed using PROC POWER in SAS.

For the first co-primary endpoint, the calculations assumed a one-sided exact binomial test, an alpha level of 0.025, a control-based rate of 0.939 with a margin of 0.12 (to derive the performance goal of 0.819), a true survival rate for OCST™ of 0.939, and desired power of 90%. Based on these specifications, the required sample size was determined to be 84 transplanted recipients.

For the second co-primary endpoint, the calculations assumed a one-sided exact binomial test, an alpha level of 0.025, a performance goal of 0.54, a utilization rate of 72% for OCST™, and desired 90% power. Based on these specifications, the required sample size was determined to be 84 transplanted recipients

In order to ensure that a sufficient number of subjects are evaluable in the per-protocol population of the trial, 90 transplanted recipients in the study is expected to provide adequate power to evaluate the two co-primary effectiveness objectives given the assumptions described.

Due to multiple primary endpoints, the Hochberg Method⁵⁵ will be used to control familywise error. The p-values for each of the co-primary endpoints will be ordered from highest to lowest. If the highest p-value is less than 0.025 then both endpoints achieve statistical significance and the null hypothesis of each co-primary endpoint can be rejected. If not, then the lower of the two p-values will be assessed against a significance level of 0.0125. If the adjusted significance level of 0.0125 is applied to any of the co-primary endpoints, the power of that analysis will be greater than 85%. Therefore, the study will be considered successful in either of the two scenarios described above.

With regard to the primary safety endpoint, the pre-specified safety margin of 0.7 events per patient, the estimated mean of 0.29 events per patient (with an estimated standard deviation of 2.0), a one-sided alpha of 0.025, and the sample size of 90 transplanted recipients results in power greater than 90% when considering a one-sample t-test on the mean.

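### The stated power above 85% at the 0.0125 level holds with 90 evaluable recipients, but for survival it does not hold after one to four Per-Protocol exclusions

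*SAP*

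**What the plan says.** SAP 3.4, Protocol 9.7 and the Protocol Synopsis (Determination of Sample Size) carry the same reasoning. Each co-primary endpoint is sized at 84 for 90% power. For survival, "For the first co-primary endpoint, the calculations assumed a one-sided exact binomial test, an alpha level of 0.025", with a performance goal of 0.819 and a true rate of 0.939. The utilization calculation uses the same test and level, with "a performance goal of 0.54, a utilization rate of 72" percent. Enrolment is set at 90 transplanted recipients so that enough are evaluable Per-Protocol.

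The Hochberg method follows. If the larger p-value is not below 0.025, "the lower of the two p-values will be assessed against a significance level of 0.0125". Protocol 9.7 then states: "If the adjusted significance level of 0.0125 is applied to any of the co-primary endpoints, the power of that analysis will be greater than 85" percent. SAP 3.4 likewise says that at this level "the power of that analysis will be greater than 85" percent. No sample size goes with that figure. The next sentence concludes from it that the study counts as successful on either route.

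Protocol 9.2.2 and SAP 6.2 make the Per-Protocol population primary for effectiveness. They list five grounds for exclusion: recipient eligibility, donor eligibility, inadequate post-transplant assessments, departure from the device instructions, and failure to meet the lung acceptance criteria.

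**The concern.** The power figure is offered without qualification, for either endpoint, in support of the fallback route, on which a single endpoint significant at 0.0125 is enough for success. A reader will take it to hold at whatever size the primary analysis has. That size is the Per-Protocol count, which the plan expects may be below 90, and no Per-Protocol minimum is given. If the figure holds at 90 but not just below it, the plan overstates what the survival test delivers on that route and hides how sensitive the test is to one or two exclusions. At stake is the accuracy of a pre-specified operating characteristic. Type I error and the validity of the Hochberg step are not affected.

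**Working it through.** **Inputs** (SAP 3.4, same in Protocol 9.7)
- Survival: null p0 = 0.939 − 0.12 = 0.819; true rate p1 = 0.939.
- Utilization: p0 = 0.54; p1 = 0.72.
- Test: one-sided exact binomial, at 0.025 for sizing and 0.0125 for the fallback step.
- Sizes: 84 required, 90 enrolled.

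**Formulas.** With X binomial, the critical count r is the smallest r for which P(X ≥ r | n, p0) ≤ α. Power is P(X ≥ r | n, p1).

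**Step 1: reproduce the plan's 84 at 0.025.**
- Survival: n = 83 gives r = 76 and power 86.7%; n = 84 gives r = 76 and power 93.0%.
- Utilization: n = 83 gives r = 55 and power 89.9%; n = 84 gives r = 55 and power 92.5%.

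For both endpoints, 84 is the smallest size from which exact power stays at or above 90%. The method therefore matches the plan's.

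**Step 2: reproduce the figure above 85% at 0.0125 with n = 90.**
- Survival: r = 82, attained level 0.0116, power 90.2%.
- Utilization: r = 60, attained level 0.0100, power 89.2%.

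The figure is reproduced for both endpoints at 90.

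**Step 3: survival at 0.0125 over Per-Protocol sizes 84 to 90.**

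| Evaluable n | Critical count | Deaths allowed | Attained level | Power | Above 85%? |
|---|---|---|---|---|---|
| 84 | 77 | 7 | 0.0097 | 86.0% | yes |
| 85 | 78 | 7 | 0.0086 | 85.3% | yes |
| 86 | 79 | 7 | 0.0076 | 84.6% | no |
| 87 | 80 | 7 | 0.0067 | 83.9% | no |
| 88 | 81 | 7 | 0.0060 | 83.2% | no |
| 89 | 82 | 7 | 0.0053 | 82.4% | no |
| 90 | 82 | 8 | 0.0116 | 90.2% | yes |

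The shortfalls from 85% are 0.4, 1.1, 1.8 and 2.6 points at n = 86, 87, 88 and 89.

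The cause is visible in the third column. From 84 to 89 the test allows seven deaths, so each added recipient makes the criterion harder to meet and power falls. At 90 it allows eight and power jumps. The critical count at 90 is 82 at both 0.025 and 0.0125, so at exactly that size the stricter level costs no survival power. Going from 90 to 89 raises the chance of missing significance, under the assumed true rate, from 9.8% (100 − 90.2) to 17.6% (100 − 82.4).

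Using 169/180 in place of 0.939 changes no conclusion: power is 82.3% at 89 and 90.1% at 90.

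**Step 4: utilization at its own denominator.** Protocol 4.1 and SAP 4.1 divide by eligible donor lungs instrumented, not by recipients. Assume 72% utilization and that every accepted lung pair is transplanted.
- 90 transplants: 90 / 0.72 = 125 instrumented. At 0.0125, r = 81 and power is 96.9%.
- 84 transplants: 84 / 0.72 ≈ 117 instrumented. At 0.0125, r = 76 and power is 96.2%.

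**The case against.** The strongest defence is that the sentence is true at the size the plan intends. The nearest sample size before it is 90 transplanted recipients, and the safety power paragraph after it also uses 90. At 90 the figure holds for both endpoints with room to spare. This stands: the number is not a miscalculation, and the defect is that no sample size is attached.

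A second defence is that no section sets a Per-Protocol range or an expected exclusion rate, and that 84 is the required size at 0.025 rather than a declared minimum at 0.0125. This also stands. A reader might infer from the table that the figure fails at most of the sizes the plan allows, since four of the seven sizes miss. That count depends on an inferred range and treats its sizes as equally likely, so the documents do not support it as a headline.

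A third defence is that the misses are small and are a saw-tooth effect of the exact test. That is correct. The exact test is nevertheless the one the plan names, and its steps are what the trial would face. A null-variance normal approximation gives survival power of 83.9% at 84, 84.5% at 85 and 85.2% to 87.5% at 86 to 90. It moves the misses to other sizes and is not the planned analysis.

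A reader might also infer a utilization shortfall, because exact power at n = 84 is 83.4% (critical count 57) and the plan gives 84 transplanted recipients as the required size for that endpoint. The documents do not support this. With the denominator they define, 84 transplants from 84 instrumented lung pairs would mean 100% utilization, which contradicts the 72% on which power is computed.

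What remains against the plan is narrow: survival is tested on Per-Protocol recipients, and one to four exclusions from 90 take power below the stated figure.

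**Conclusion.** The sentence needs qualifying; it is not wrong throughout. Exclusions from the primary population are something the plan itself provides for, so an unqualified survival power above 85% is not reliably delivered there. The lowest value between 84 and 90 evaluable recipients is 82.4%.

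This rests on the plan's assumed true survival of 0.939, on the exact binomial test, on reading 84 to 90 as the likely Per-Protocol range, and on the Hochberg step in SAP 3.4 being the rule that applies. SAP 5.5 says no multiplicity adjustment will be made, which has to be reconciled separately.

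Severity is minor. A reader might conclude that the trial is undersized or that the fallback success rule is undermined. Neither follows: at 0.025, survival power stays above 90% at every size from 84 to 90, and the error control of the Hochberg step does not depend on its power.

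**What to change.** In the Protocol Synopsis, Protocol 9.7 and SAP 3.4, replace the sentence with one that names its sample sizes, for example: *At the 0.0125 level, survival power is 90% with 90 evaluable recipients and ranges from 82% to 90% over Per-Protocol sizes of 84 to 90. Utilization power at that level is about 97% with about 125 eligible instrumented donor lungs, assuming 72% utilization and 90 transplants.*

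The cost is one reworded passage in each of the three places and a slightly less favourable survival figure. Enrolment, significance levels, critical counts and hypotheses stay as they are.
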